## Treatment Schema

## Precis

### Background

- Saracatinib is a potent and selective Src kinase inhibitor.
- In vitro studies demonstrate that 95% of patients with osteosarcoma have activation of Src, or one of its substrates.
- A Phase I study of saracatinib, given daily, in adult patients with advanced solid malignancies, has identified 175 mg as the maximum tolerated dose.

### Primary Objective

- To determine if the addition of saracatinib to pulmonary metastasectomy, versus placebo and pulmonary metastasectomy, results in an increase in progression free survival.

### Secondary Objectives

- To determine if the addition of saracatinib to pulmonary metastasectomy, versus placebo and pulmonary metastasectomy, results in an increase in overall survival.
- To determine if the addition of saracatinib to pulmonary metastasectomy, versus placebo and pulmonary metastasectomy, results in an increase in the time to treatment failure, defined as a composite endpoint measuring time from randomization to discontinuation of treatment for any reason, including disease progression, treatment toxicity, or death.
- To perform microarray analysis of tumor samples to identify a gene signature that predicts for recurrence of osteosarcoma.
- To evaluate tumor samples for biomarkers related to activation of Src and Src substrates.
- To establish cell lines and murine xenografts from recurrent tumor samples.
- To perform sequencing analysis of DNA and RNA in tumor samples compared to normal blood to detect mutations that may be causative for recurrent osteosarcoma.

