different treatments, including surgery alone, and/or radiation, and/or chemotherapy, and/or high dose chemotherapy with stem cell rescue. Therefore, historical data do not give a true indication of actual survival rates. This study will try to determine whether patients who receive saracatinib will experience a 60% relative increase in progression free survival. Secondary objectives will determine whether patients who receive saracatinib will experience a 56% relative increase in overall survival and an increase in the time to treatment failure. Any adverse event, including toxicity, disease progression and death, that result in discontinuation of either saracatinib or placebo will be considered a treatment failure. The randomized nature of this study will allow us to determine the actual survival rates in these two cohorts, thereby assessing the efficacy of saracatinib in this patient population. Forty-four patients will need to be randomized in each arm, for a total of 88 patients, over a 48-month accrual period. Follow-up for survival of the last patient randomized must continue for an additional year. Patients who recur in the lung while on-study and who are thought to be amenable to complete surgical resection will be unblinded. Those who were receiving placebo will be given the option of undergoing surgical resection. If fully resected, they will be given the option to begin oral therapy with saracatinib.

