24 months	history, physical, vital signs, laboratory tests thoracic CT
30 months	history, physical, vital signs *
36 months	history, physical, vital signs, laboratory tests thoracic CT

Laboratory tests are as follows:

- white blood cell count with differential
- hemoglobin and hematocrit
- platelet count
- sodium, potassium, chloride, bicarbonate, blood urea nitrogen, creatinine, glucose
- calcium, magnesium, phosphorus
- ALT, AST, total bilirubin,
- alkaline phosphatase, lactate dehydrogenase, total protein, albumin

\* At the discretion of the treating physician, these visits do not need to be performed at the study center. However, a document containing the interim history, physical examination, weight and height, vital signs, laboratory tests, and CT scan results when appropriate, must be sent to the treating physician at the study center as soon as they are available.

\*\* The purpose of the two additional thoracic CT scans is to monitor for interstitial lung disease, which has been seen in 2% of patients taking saracatinib. If there is any suspicion of interstitial lung disease on any CT scan, the patient must undergo high-resolution CT imaging to exclude interstitial lung disease. Any evidence of interstitial lung disease will lead to removal of the patient from the study (defined in the Exclusion Criteria in Section 2.1.2.f). The suggested parameters for the high-resolution thoracic CT scan are as follows: position (supine), slice thickness ( $\leq 1.25$  mm), slice spacing (10 mm), start location (10 mm below the apices), end location (10 mm above the costophrenic angles).

\*\*\* Previous studies have not demonstrated prolonged QTc intervals in patients treated with saracatinib. A 12-lead EKG should be obtained after the patient has rested in a supine position for at least five minutes. The treating physician should review the EKG. Any abnormality of clinical significance should result in medical management of the patient as clinically indicated. The abnormality should be reported as an adverse event or a serious adverse event (see Section 7.2).

\*\*\*\* Saracatinib or placebo will be discontinued after thirteen 28-day cycles (364 days) of therapy.

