diagnosis, the earliest date of the abnormal radiologic finding will be used as the ending date for measurement of progression free survival and time to treatment failure. Any adverse event that results in discontinuation of either saracatinib or placebo will be considered a treatment failure. This includes toxicity, disease progression or death. The time to treatment failure will begin on the day of randomization, and end on the day of discontinuation of either saracatinib or placebo.

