## **5.3 Statistical Considerations**

The primary goal of this study is to determine whether the addition of saracatinib to surgery will result in an improvement in progression free survival (PFS). The sample size will be based on being able to detect a 60% relative improvement (from 33% to 53%) in PFS probability at two years. The current 2-year PFS probability is 33%, when a second surgical complete remission is achieved (3). Assuming exponential survival curves, the hazard rate corresponding to this 2-year PFS probability for the control arm is 0.0462, which is defined as approximately a 0.0462 probability of failing each month when the 2-year PFS probability is 33%. If we assume that the 2-year PFS probability may be 53% for the saracatinib arm, the hazard is 0.0265, which then results in a hazard ratio of 1.75. Forty-four patients will need to be randomized in each arm of the study, for a total of 88 patients, over a 48-month accrual period. Follow-up of the last patient randomized must continue for an additional year. Since this study follows a phase II.5 design (35), this provides 80% power to detect a difference between the two resulting actuarial curves with a one-sided 0.10 alpha level log-rank test.

A secondary goal of this study is to determine whether the addition of saracatinib to surgery will result in an improvement in overall survival (OS). The sample size selected to evaluate PFS will also be adequate to detect a 56% relative improvement (from 45% to 70%) in OS probability at three years. The current 3-year OS probability is 45%, when a second surgical complete remission is achieved (3). Assuming exponential survival curves, the hazard rate corresponding to this 3-year OS probability for the control arm is 0.0222, which is defined as approximately a 0.0222 probability of failing each month when the 3-year OS probability is 45%. If we assume that the 3-year OS probability may be 70% for the saracatinib arm, the hazard is 0.0099, which then results in a hazard ratio of 2.24. Evaluation of the 88 patients who are randomized, over the same time frame, will provide 85% power to detect a difference between the two resulting actuarial curves with a one-sided 0.10 alpha level log-rank test.

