As explained in section 3.2.6, a subset of patients who recur while receiving placebo will be given the opportunity to receive saracatinib. Since patients on both arms will have received this agent, although at different times in the natural history of their disease, this may result in a lessening of the difference in survival between the arms compared to the case when only patients on one arm received the agent. However, since development of a recurrence may still be associated with overall survival duration, the magnitude of the impact may be limited.

An additional secondary goal is to determine if the addition of saracatinib to pulmonary metastasectomy, versus placebo and pulmonary metastasectomy, results in an increase in the time to treatment failure (TTF). Any adverse event that results in discontinuation of either saracatinib or placebo will be considered a treatment failure. This includes toxicity, disease progression or death.

Again, the randomized nature of the Phase II.5 study will allow us to determine the actual 2-year PFS and 3-year OS rates in patients who receive surgery and placebo, or surgery in combination with saracatinib.

Patients will be stratified based on the following criteria:

Number of Recurrences: FIRST versus SECOND versus THIRD or MORE

Number of Recurrent Nodules: ONE or TWO versus THREE or MORE

The date that the patient is randomized will be used as the starting date for measurements of overall survival, progression free survival and time to treatment failure. Progressive disease will be defined as recurrence of osteosarcoma based on radiographic evidence or histologic verification of the recurrent lesion.

At the first annual opportunity following the point at which 20 patients per arm have been randomized (40 total) and potentially followed for at least 12 months, an interim evaluation for futility will be performed.

The futility evaluation will be performed as follows. Based upon the full data available at that time, a conditional power analysis will be performed to determine if the trial is

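### The definitions of time to treatment failure conflict on whether finishing the planned 13 cycles is a failure, and no rule says how completers are handled

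*Combined protocol and SAP*

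**What the plan says.** The Precis (Secondary Objectives) is the only place that formally defines TTF: a "composite endpoint measuring time from randomization to discontinuation of treatment for any reason", with progression, toxicity and death named among the reasons. Section 1.1.2 repeats the objective without a definition. Section 3.7.1 starts TTF at randomization and has it "end on the day of discontinuation of either saracatinib or placebo".

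The planned end of therapy is described in the same terms. Section 3.4 states: "Saracatinib or placebo will be discontinued after thirteen 28-day cycles (364 days) of therapy". The Section 3.4 visit schedule and the Appendix A footnotes say the same.

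Three sections describe the event more narrowly. Section 5.3 says "Any adverse event that results in discontinuation of either saracatinib or placebo will be considered a treatment failure" and adds "This includes toxicity, disease progression or death". Section 3.7.1 carries the same two statements. Section 1.2.9 says that adverse events, among which it lists toxicity, progression and death, "that result in discontinuation of either saracatinib or placebo will be considered a treatment failure".

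Section 3.3.2 does give a handling rule for toxicity withdrawals: failures for TTF, censored for PFS. There is no matching rule for patients who complete treatment. Section 5.3 states no test, hazard assumption or power for TTF.

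**The concern.** A patient who takes all 13 cycles without recurrence is a treatment success. Under the Precis wording that patient is a failure at about day 364. Under the narrower wording the patient is not a failure, but the text does not say when follow-up for TTF ends.

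Take a patient who completes 13 cycles and recurs at month 18. The text supports three values:

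- an event at about day 364, from the Precis definition;
- a censored time at about day 364, from the narrow event list, with the censoring left unstated;
- an event at month 18, because Section 3.7.1 also makes the first abnormal scan the end date for TTF.

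The analyst must choose, possibly after seeing data. The choice affects most of the trial, and it affects the arms unequally, because the better arm has more completers.

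**Working it through.** **Inputs.** Section 5.3 gives 44 patients per arm ("for a total of 88 patients, over a 48-month accrual period"), one further year of follow-up, two-year PFS of 33% and 53%, hazards of 0.0462 and 0.0265 per month, a hazard ratio of 1.75, one-sided alpha of 0.10, and one-year PFS of 57.4% and 72.8%. Section 3.4 gives 364 days of therapy.

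**Reproducing the plan's figures.** The hazards are −ln(0.33)/24 = 0.0462 and −ln(0.53)/24 = 0.0265. One-year PFS is exp(−12 × 0.0462) = 57.4% and exp(−12 × 0.0265) = 72.8%. With uniform accrual over 48 months plus 12 months of follow-up, the event probability per arm is 1 − [exp(−12h) − exp(−60h)]/(48h). This gives 33.8 + 25.9 = 59.7 PFS events. Schoenfeld power is Φ(√59.7/2 × ln 1.75 − 1.2816) = 0.81, against the stated 80%. The plan's power reproduces.

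**Completers.** Assume that nobody stops except for progression or death. Then 44 × 0.574 = 25.3 placebo and 44 × 0.728 = 32.0 saracatinib patients reach the planned end, a total of 57.3 of 88 (65%). The other 88 − 57.3 = 30.7 patients (18.7 placebo, 12.0 saracatinib) fail before it. The documents give no rate of early stopping for other reasons. If 10%, 20% or 30% of would-be completers stopped early (assumed), the 57.3 becomes 51.6, 45.8 or 40.1.

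**Completers censored.** About 31 events remain. Power is Φ(√30.7/2 × ln 1.746 − 1.2816) = 0.60. Simulation of 1,500 trials also gives 60%, with a hazard ratio (saracatinib to placebo) of about 0.58.

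**Completions counted as events.** A one-sided 0.10 log-rank test is assumed here, carried over from PFS and OS. The spread in completion dates is also assumed.

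| Completion dates | Log-rank power | Cox hazard ratio |
|---|---|---|
| All on one day | 60% | 0.84 |
| Spread over 3 weeks | 38% | 0.83 |
| Spread over 6 weeks | 39% | 0.84 |

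In the tied case everyone still at risk fails together. Observed minus expected at that time is n₁ − n × n₁/n = 0, and the variance factor (n − d)/(n − 1) is also 0, so the log-rank test gains nothing and loses nothing. The Cox estimate moves even so under Efron or Breslow tie handling.

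A second simulation (2,000 trials) used the log-rank-based estimate exp((O − E)/V):

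| Assumed pattern | Completions as events | Completers censored |
|---|---|---|
| Start delay 0–7 days | power 40%, HR 0.77 | power 59%, HR 0.58 |
| Delay 0–14 days plus holds 0–21 days | power 39%, HR 0.80 | power 61%, HR 0.57 |
| As above, plus 10% toxicity stops per arm | power 35%, HR 0.82 | power 52%, HR 0.65 |

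Some spread is plausible. TTF runs from randomization, dosing starts afterwards, and Sections 3.3.2 and 3.3.3 allow holds of up to 21 and 35 days. Its size is not given.

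**The case against.** The strongest reply is that the statistical section should govern over a synopsis. Sections 5.3, 1.2.9 and 3.7.1 tie failure to toxicity, progression or death, and even the Precis follows its broad phrase with the same three examples. With the ordinary meaning of failure, this makes it clear that completion was not meant to count. A reader might infer that the protocol has a single TTF rule under which completion is a failure. The documents do not support that: they contain two incompatible descriptions. If the conflict is settled in favour of the narrow list, completion stops being an event.

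That stands, but it does not close the gap. The narrow text sits beside the formal definition without replacing it, and it never says that completers are censored or on what date.

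The reply is also right on size. The figure of 57 is an upper bound, since the removal criteria in Section 3.7 allow for toxicity, refusal, non-compliance and physician decision. The simulated delays and holds are assumptions, and the holds were drawn for every patient although Section 3.3.2 applies them to drug-related toxicity. TTF is a secondary endpoint with no stated power.

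A reader might also infer that median TTF would equal the planned treatment length whatever the drug does. That is not general. Placebo completion is 57.5% at day 364 before other stops, so early stopping of about 13% (0.575 × 0.87 = 0.50) brings the placebo median forward. With an assumed 20% it falls at about 324 to 328 days.

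**Conclusion.** The point holds as a conflict between definitions together with a missing rule for completers. It should be corrected, but it does not threaten the trial's main conclusions: PFS and OS are unaffected.

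Under the Precis reading up to about 57 of 88 patients would be scored as failures, or about 40 to 52 with an assumed 30% to 10% early stopping. With staggered completion dates the hazard ratio moves from about 0.58 to about 0.8 and log-rank power falls from about 60% to about 40%. These figures assume that the PFS hazards apply to TTF, a one-sided 0.10 log-rank test, and the spreads shown.

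It would be too strong to say that the treatment comparison is diluted in every case. If all completions fall on the same day after randomization, the log-rank test is essentially unchanged and only the event count, the Cox estimate and the descriptive summaries are affected.

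**What to change.** Use one definition in the Precis and in Sections 1.2.9, 3.7.1 and 5.3:

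- A TTF event is discontinuation of study drug before completion of the planned 13 cycles.
- Patients who complete 13 cycles are censored at their last planned dose.
- Recurrence after completion counts in PFS, not in TTF.
- The number of completers per arm is reported beside the TTF curve.

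In the same edit, confirm that refusal and administrative withdrawal count as events under this wording, reconcile the two TTF end dates that Section 3.7.1 gives for progression, and name the TTF test.

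The cost is a few sentences and no new data, since stop dates are needed for TTF in any case. The nominal event count falls to about 31 on the plan's hazards, with power of about 60%. On those hazards, with no other stops, both curves are still above 50% at day 364 (57.5% and 72.8%), so the median TTF may not be estimable in either arm. The proportion free of treatment failure at the end of planned therapy would be a more useful summary.

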### Eligibility

- Patients  $\geq 15$  and  $< 75$  years of age, with suspected recurrence of osteosarcoma, localized to the lung, are eligible for enrollment
- Patients with histological confirmation of recurrent osteosarcoma, localized to the lung, who have had complete surgical removal of all lung nodules, will be eligible for randomization.

### Design

- Only after complete resection of all lung nodules, patients will be randomized to treatment with saracatinib or placebo. Eighty-eight patients will be randomized, 44 patients in each arm of the study. This will be a multi-institutional study.

- Saracatinib, or placebo, will be administered as a once daily, oral dose of 175 mg, for a 28-day cycle, with no breaks between cycles. The duration of treatment with saracatinib or placebo will be 13 cycles (364 days total).
- Patients will begin cycle 1 after complete surgical resection.

#### Cross-Over Component

- Patients who recur in the lung while on-study and who are thought to be amenable to complete surgical resection will be un-blinded. Those patients who were receiving placebo may then have the option of undergoing surgical resection. If fully resected (staged thoracotomy is acceptable), they will be given the option of receiving oral therapy with saracatinib. Saracatinib will be administered as a once daily, oral dose of 175 mg, for a 28-day cycle, with no breaks between cycles. The duration of treatment with saracatinib will be **thirteen 28-day cycles** (364 days total).

# **1 Introduction**

## **1.1 Study Objectives**

### **1.1.1 Primary Objective**

To determine if the addition of saracatinib to pulmonary metastasectomy, versus placebo and pulmonary metastasectomy, results in an increase in progression free survival.

### **1.1.2 Secondary Objectives**

To determine if the addition of saracatinib to pulmonary metastasectomy, versus placebo and pulmonary metastasectomy, results in an increase in overall survival.

To determine if the addition of saracatinib to pulmonary metastasectomy, versus placebo and pulmonary metastasectomy, results in an increase in the time to treatment failure.

To perform microarray analysis of tumor samples to identify a gene signature that predicts for recurrence of osteosarcoma.

To evaluate tumor samples for biomarkers related to activation of Src and Src substrates.

[figure not shown]
To establish cell lines and murine xenografts from recurrent tumor samples.

## **1.2 Background and Rationale**

### **1.2.1 Recurrent Osteosarcoma**

Osteosarcoma is the most common malignant bone tumor in the United States and Europe. Historically, this was once a fatal diagnosis. However, with the increasing use of chemotherapy in the late 1970s, patients who underwent both surgery and chemotherapy had a marked improvement in survival. Currently the overall cure rate is 65%, representing a dramatic improvement over previous decades (1,2). Unfortunately, patients who recur with disease have only a 25% five-year survival rate (3,4). Approximately 33% of patients who have completed therapy for osteosarcoma will recur. In large retrospective analyses performed by the Cooperative Osteosarcoma Study Group (3) and the Rizzoli Institute (4), the only patients who survived long-term were those who achieved complete surgical removal of recurrent tumor, illustrated in the survival curve

on the right (3). Specifically, 291 patients did not achieve surgical remission, and none of these patients survived long-term. In contrast, 512 patients achieved surgical remission and five-year overall survival rates were 38% and 30% in the two studies. These patients received either multi-agent, single agent or no chemotherapy, but they shared the common feature that everyone had achieved a second surgical remission. It did not appear that the addition of adjuvant treatment increased survival (40% survival with chemotherapy versus 35% survival without chemotherapy,  $p=0.35$ ) (3). However, this trend may eventually prove to be statistically significant in larger cohorts. Conversely, for those treated with chemotherapy or radiation therapy only without surgery, there were no survivors (4).

One of the significant prognostic factors that predicts for long-term survival is the number of nodules at the time of recurrence. In the Cooperative Osteosarcoma Study Group study, patients who had one nodule had a 38% 5-year overall survival rate, compared to 15% for patients with two or more nodules ( $p<0.01$ ) (3). Comparably, in the Rizzoli Institute study, patients who had one or two nodules had a 44% 5-year event free survival rate, compared to 22% for patients with three or more nodules ( $p<0.01$ ) (4).

Another factor that impacts outcome is the number of recurrences. The only study that has examined these subsets of patients is the retrospective analysis performed at the Rizzoli Institute (4). The following shows the number of long-term survivors as a percentage of those who were able to obtain surgical remission. First relapse – 30.6% (53 of 173 patients). Second relapse – 25.9% (14 of 54 patients). Third relapse – 16.7% (2 of 12 patients). Ten patients had a fourth relapse and six of these patients achieved surgical remission. However, all six patients progressed to have a fifth relapse. Not surprisingly, patients have decreased survival probability when they have multiple recurrences.

The role of chemotherapy in the treatment of recurrent osteosarcoma is unclear. To date, there have not been any randomized studies that have evaluated the benefit of chemotherapy in this setting. However, multiple Phase II studies have failed to show improvement in outcome. Several of these include the use of cyclophosphamide and topotecan (5), docetaxel (6), ecteinascidin 743 (7), as well as imatinib mesylate (8). The latter is a potent inhibitor of the abl receptor tyrosine kinase family, including platelet-derived growth factor receptor and KIT kinase, but is a poor inhibitor of Src. The use of high-dose chemotherapy followed by stem cell rescue showed that induction of complete remission was feasible, but that treatment outcomes were not improved (9,10).

A report from the Children’s Cancer Group showed a small increase in overall response following treatment with ifosphamide, carboplatin and etoposide, however, the result was not statistically significant (11). A retrospective report from the Memorial Sloan-Kettering Cancer Center suggested a benefit from the addition of high-dose ifosphamide following surgery, but the result did not reach statistical significance (12). The use of

[figure not shown]
high-dose ifosfamide for recurrent osteosarcoma at the M.D. Anderson Cancer Center resulted in 30% (5/16 patients) disease-free survival (13). However, three of these patients had not previously received ifosfamide. In addition, four patients developed renal toxicity, two of which, progressed to acute renal failure. To date, there has not been a study of sufficient size to justify the use of high-dose ifosfamide in this setting.

Unfortunately, these results show that there is no effective salvage regimen for patients with recurrent osteosarcoma. Therefore, the current standard of care is to resect the recurrent tumor if possible, followed by observation. If any chemotherapeutic agent with activity against osteosarcoma (adriamycin, cisplatin, ifosfamide, methotrexate) was not used during treatment of the primary tumor, then that agent may be administered as adjuvant therapy following surgical resection. Unfortunately, even those patients who achieve complete surgical remission have only a 35% long-term survival rate. All of these factors point to the importance of identifying new biological agents for the treatment of recurrent osteosarcoma.

